16.5 Trial Records Retention

Trial records will be maintained for at least three years from the date that the grant federal financial report (FFR) is submitted to the NIH (or 2 years following the date that SDF is approved for the drug indication for which it is being investigated, whichever is longer).

Trial documents should be retained for a minimum of 2 years after the last approval of a marketing application in an ICH region and until there are no pending or contemplated marketing applications in an ICH region or until at least 2 years have elapsed since the formal discontinuation of clinical development of the investigational product. These documents should be retained for a longer period, however, if required by local regulations. No records will be destroyed without the written consent of the sponsor, if applicable. It is the responsibility of the sponsor to inform the investigator when these documents no longer need to be retained.

16.6 Protocol Deviations

A protocol deviation is any noncompliance with the clinical trial protocol or Good Clinical Practice requirements. The noncompliance may be on the part of the participant, the investigator, or trial staff. As a result of deviations, corrective action plans are to be developed by the trial staff and implemented promptly.

Protocol deviations include, but are not limited to the following:

- Outcome measurement (e.g., caries exam) not performed, trial drug/placebo not applied
- Missed visit, or visit out of window

In addition, non-compliance issues or violations that will be expected to be reported include, but may not be limited to:

- Failure to obtain participant Informed Consent
- Failure to obtain IRB approval and keep IRB approval up to date
- Failure to follow IRB recommendations

These practices are consistent with investigator and sponsor obligations in ICH E6:

- Compliance with Protocol, Sections 4.5.1, 4.5.2, 4.5.3, and 4.5.4.
- Quality Assurance and Quality Control, Section 5.1.1
- Noncompliance, Sections 5.20.1 and 5.20.2.

All deviations from the protocol must be addressed in trial participant source documents and will be periodically reported to NIDCR and the local IRB, according to their requirements. Protocol deviations and violations will be recorded in the eCRFs. Additionally, all protocol deviations and violations will be routinely reported to the DSMB.

17 PUBLICATION/DATA SHARING POLICY

This trial will comply with the *NIH Public Access Policy*, which ensures that the public has access to the published results of NIH funded research. It requires scientists to submit final peer-reviewed journal manuscripts that arise from NIH funds to the digital archive PubMed Central upon acceptance for publication.

The International Committee of Medical Journal Editors (ICMJE) member journals have adopted a clinical trials registration policy as a condition for publication. The ICMJE defines a clinical trial as any research project that prospectively assigns human subjects to intervention or concurrent comparison or control groups to trial the cause-and-effect relationship between a medical intervention and a health outcome. Medical interventions include drugs, surgical procedures, devices, behavioral treatments, process-of-care changes, and the like. Health outcomes include any biomedical or health-related measures obtained in patients or participants, including pharmacokinetic measures and adverse events. The ICMJE policy requires that all clinical trials be registered in a public trials registry such as *ClinicalTrials.gov*, which is sponsored by the National Library of Medicine. Other biomedical journals are considering adopting similar policies. For interventional clinical trials performed under NIDCR grants and cooperative agreements, it is the grantee's responsibility to register the trial in an acceptable registry, so the research results may be considered for publication in ICMJE member journals. The ICMJE does not review specific studies to determine whether registration is necessary; instead, the committee recommends that researchers who have questions about the need to register err on the side of registration or consult the editorial office of the journal in which they wish to publish.

U.S. Public Law 110-85 (Food and Drug Administration Amendments Act of 2007 or FDAAA), Title VIII, Section 801 mandates that a "responsible party" (i.e., the sponsor or designated principal investigator) register and report results of certain "applicable clinical trials:"

Trials of Drugs and Biologics: Controlled, clinical investigations, other than Phase I investigations, of a product subject to FDA regulation;

Trials of Devices: Controlled trials with health outcomes of a product subject to FDA regulation (other than small feasibility studies) and pediatric post market surveillance studies.

NIH grantees must take specific *steps to ensure compliance* with NIH implementation of FDAAA.

1. Activity Working Definitions and Criteria

- An Active Lesion is considered to have a great likelihood of transition or change (progress, arrest or regress).
- An Inactive (Arrested) Lesion is considered to have stopped, and thus not likely to transition overtime.

Clinical observations to be taken into consideration for assessing lesion activity are based on a modification of the Nyvad et al. (1999) caries lesion activity assessment criteria and include visual appearance, tactile feeling and potential for plaque accumulation, depending on the severity (i.e., ICDAS score) of the lesion. When in doubt score the lesion as active.

Note that for this trial lesions being targeted for inclusion and SDF/placebo application are ICDAS 5 and 6 lesions (see next page); that are active (see table below), and do not cause pain due to caries at baseline, or have pulp exposure, mobility not associated with expected exfoliation patterns, or signs of pulpal infection (abscess, fistula, swelling). Change in lesion activity is the primary trial outcome.

See table below for activity lesion criteria relevant to ICDAS 5 and 6 lesions *

ICDAS Score	Characteristics of the Lesion	
	Active Lesion	Inactive (Arrested) Lesion
1, 2 and 3	Surface of enamel is whitish/yellowish, opaque with loss of luster; feels rough when the tip of the probe is moved gently across the surface. Lesion is in a plaque stagnation area, i.e., pits and fissures, near the gingival margin, and proximal below the contact point	Surface of enamel is whitish/brownish or black. Enamel may be shiny and feels hard and smooth when the tip of the probe is moved gently across the surface. For smooth surfaces, the caries lesion is typically located at some distance from the gingival margin
4	Probably active	
* 5 and 6	Dentin in cavity feels soft/leathery on gently probing (probe penetrates dentin).	Dentin in cavity may be shiny and feels hard on gentle probing.

<https://www.icdas.org/uploads/ICDAS%20Criteria%20Document%20corrected%202013.pdf>

2. Surface Code-Severity Scoring System

The data collected will be twofold – Tooth and Surface Code.

- The Tooth Code is indicated by using one of the following codes: S = Sound; U = Unerupted; X = Extracted, presumed for the reason of caries; Y = Extracted for other reasons, not caries; N = Not gradable, e.g., for reasons of trauma; and C = Caries or caries related events such as fillings.
- The Surface Code is indicated when the tooth code of caries is present. Tooth codes include the ICDAS lesion severity and filling code scoring system:

Filling and Sealant Codes

- 1 = Sealant, partial
- 2 = Sealant, full
- 3 = Tooth colored restoration
- 4 = Amalgam restoration
- 5 = Stainless steel crown
- 6 = Crown, gold, porcelain or MCC
- 7 = Lost restoration
- 8 = Temporary restoration
- 9 = Other

ICDAS Caries Severity Codes (Example images in primary teeth are provided in the next page)

Code	Narrative	Description
0	Sound tooth surface	No or questionable change in enamel translucency after prolonged air drying (>5s). Artifacts such as hypoplasias, fluorosis, wear and stains must be avoided
1	First visual change in enamel	Opacity or discoloration not visible on the wet surface, but distinctly visible after air drying, or changes seen on a wet surface, but limited to the confines of the pit and fissure area
2	Distinct visual change in enamel	Opacity or discoloration distinctly visible on a wet surface and/or wider than the fissure/fossa area
3	Localized enamel breakdown due to caries with no visible dentin	Initial, localized enamel breakdown in opaque or discolored enamel at the entrance to or within the pit and fissure, appearing substantially and unnaturally wider than normal, but dentin not visible clinically in the walls or the base of the cavity/discontinuity. If in doubt, or to confirm the visual assessment the probe can be used gently across the surface to confirm the presence of a cavity, by gently sliding the tip along the suspect pit and fissure
4	Cavitated or Non-cavitated surface with underlying dark shadow from dentin	Shadow of discolored dentin (gray, blue or brown) visible through an apparently intact enamel (most easily seen when wet)
*5	Distinct cavity with visible dentin	Cavitation in opaque or discolored enamel clearly exposing clinically the dentin beneath. The cavity involves less than half of the surface of the tooth
*6	Extensive distinct cavity with visible dentin	Obvious loss of tooth structure, the cavity is both deep and wide, and dentin is clearly exposed clinically and visible on the walls and at the base of the cavity, revealing an extensive cavitation. The cavity involves half or more of the surface of the tooth

When in doubt between 2 scores, choose the lower score.

***Note that for this trial lesions being targeted for SDF/placebo application are ICDAS 5 and 6 lesions (with cavitations exposing dentin clinically; see table above for criteria relevant to ICDAS 5 and 6 lesions).**

As air drying will not be used in this trial, only drying with cotton or gauze, ICDAS 1 lesions that are white may not be able to be distinguished.

Example Images in Primary teeth	ICDAS Severity Score
 	0- Sound tooth surface
	1- First visual change in enamel
 	2- Distinct visual change in enamel
 	3- Localized enamel breakdown due to caries with no visible dentin
	4- Underlying dark shadow from dentin +/- localized enamel breakdown (no dentin exposed clinically)
	* 5- Distinct cavity with visible dentin clinically
 	* 6- Extensive distinct cavity with visible dentin clinically

**Note that for this trial lesions being targeted for SDF application are ICDAS 5 and 6 lesions (see table above for examples of ICDAS 5 and 6 lesions in primary teeth. These can be in anterior or posterior teeth.)*

Appendix B: Dental Discomfort Questionnaire (DDQ)

(Versloot et al., 2006)

This validated questionnaire consists of two parts.

A. The first part includes a question concerning the occurrence of toothache.

1. The parent/guardian is asked if he/she ever noticed that the child had toothache: Have you noticed if your child currently has a toothache?

This question can be answered with: 'never', 'sometimes', 'often', or 'I do not know'.

2. If the parent/guardian answers 'sometimes' or 'often', they are asked when.

Choices include: either during meals, during daytime or nighttime (several alternatives possible).

B. The second part of the DDQ consists of 8 validated questions about different behaviors associated with toothache or discomfort due to caries (e.g., crying during meals or chewing problems) and two additional standard of care questions for the study's pediatric clinics:

1. Problems with brushing upper teeth
2. Puts away/avoids something nice to eat
3. Problems with brushing lower teeth
4. Bites with molar instead of front teeth
5. Chewing at one side
6. Problems chewing
7. Reaching for the cheek while eating
8. Crying during meals

In addition, we will ask the following questions about behaviors associated with toothache that are used as standard of care in the pediatric clinics at the three clinical sites:

9. Wakes up in the middle of the night with a toothache
10. Has a toothache that lasts for more than 1 hour

For each item the parent/guardian is asked to rate how often their child shows a given specific behavior. The questions can be answered on a three-point scale: 0 'never', 1 'sometimes', and 2 'often'.

Note: A DDQ score of 1 or higher (i.e., any level of toothache complaint) at baseline will result in exclusion of participant from the trial.

Once a tooth is included in the trial and treated, a DDQ score of 1* or higher, which the examiner can associate during a clinical visit with a trial tooth, will result in exiting of tooth from the trial, and arranging follow-up care for the tooth (note there might be other reasons for exiting a tooth from the trial, such as abscess, mobility, etc. Refer to Exiting Rules).

During intermediate phone calls, a toothache DDQ score of 1 or higher will trigger the trial team to attempt an unscheduled/emergency clinical visit (Note: we expect these numbers to be low, because during a 6-9 month hospital operating room waiting period in teams' clinics to treat children with S-ECC, only 8-12% of patients required emergency visits due to complaints of toothache pain).

*According to Versloot et al. (2006), 70% of children with cavities and toothache had a DDQ score of 4 or higher, and the average score for these children was 5.73. However, for ethical reasons in this trial, any complaint of toothache pain (DDQ score of 1 or higher) will require an action from the trial team as described above.

Appendix C: Oral Health-Related Quality of Life (OHRQoL) Questionnaires
Short-form Parental-Caregiver Perception Questionnaire (P-CPQ) and Family Impact Scale (FIS) Questionnaires
(Thomson et al., 2013)

This document contains the 16-item short-form version of the P-CPQ, together with the 8-item short-form version of the FIS. All have been validated.

Please note: these two short-form questionnaires should be used with the following “Global Measures” questions (which serve as an important validity check; Thomson et al., 2013)

1. Parent/Family Global Measures Questions

These questions are about your child’s oral health:

1-How would you describe the health of your child’s teeth and mouth?				
Excellent	Very Good	Good	Fair	Poor
2-How much is your child’s overall well-being affected by the condition of his/her teeth, lips, jaw or mouth?				
Not at all	Very Little	Some	A lot	Very much
3-How much is your family’s daily life affected by your child’s teeth lips, jaws or mouth?				
Not at all	Very Little	Some	A lot	Very much

Note: A global item is always used alongside any multi-item scales, such as the P-CPQ and the FIS, because it acts as a concurrent validity check. For the P-CPQ, the accepted single-item global question is number 2 above. For the FIS, the accepted single-item global question is number 3 above. For the P-CPQ, for example, we need to check that, at baseline, the mean P-CPQ scale scores show an ascending gradient across the 5 response categories of the global question. This is an essential step, because to investigate how the OHRQoL of the child participants has changed, we need to first reassure ourselves that the P-CPQ is performing adequately in a cross-sectional sense in this population (and the same applies to the FIS and the other global question).

Global transition judgment question (to be provided only at 3-, 6- and 8-month follow-up visits)

Since your child’s teeth had the SDF/placebo treatment is your child’s overall well-being				
Much improved	A little improved	The same	A little worse	Much worse

Note: This global transition judgment question will be included at follow-up visits for assessing the responsiveness of the OHRQoL measures in children with ECC (Locker et al., 2004). If the use of SDF had improved the participants’ lives, we would expect to see a substantial fall in P-CPQ scores between baseline and follow-up in the children who had received the SDF. This will be determined using the effect size, a unitless measure of change in mean score which is calculated by subtracting the follow-up score from the baseline score and dividing the result by the standard deviation of the mean baseline score for that group. This global transition judgment (which is a single question which basically asks them to judge whether they got better, got worse or stayed the same) serves both as a concurrent validity check for the change in P-CPQ score (in the same way that the global item earlier serves as a concurrent validity check at baseline, as described above) and also as an outcome measure in its own right.

2. P-CPQ 16-item version

The following questions ask about symptoms and discomfort that children may experience due to the condition of their teeth, lips, mouth and jaws.

During the last 3 months, how often has **YOUR CHILD**:

Had pain in the teeth, lips, jaw or mouth?

Never	Once or twice	Sometimes	Often	Every day or almost every day	Don't know
-------	---------------	-----------	-------	-------------------------------	------------

Had food stuck in the roof of the mouth?

Never	Once or twice	Sometimes	Often	Every day or almost every day	Don't know
-------	---------------	-----------	-------	-------------------------------	------------

Had bad breath?

Never	Once or twice	Sometimes	Often	Every day or almost every day	Don't know
-------	---------------	-----------	-------	-------------------------------	------------

Had food caught in or between the teeth?

Never	Once or twice	Sometimes	Often	Every day or almost every day	Don't know
-------	---------------	-----------	-------	-------------------------------	------------

Had difficulty biting or chewing firm foods such as fresh apple, corn on the cob or firm meat?

Never	Once or twice	Sometimes	Often	Every day or almost every day	Don't know
-------	---------------	-----------	-------	-------------------------------	------------

Had trouble sleeping?

Never	Once or twice	Sometimes	Often	Every day or almost every day	Don't know
-------	---------------	-----------	-------	-------------------------------	------------

Has taken longer than others to eat a meal?

Never	Once or twice	Sometimes	Often	Every day or almost every day	Don't know
-------	---------------	-----------	-------	-------------------------------	------------

Had difficulty drinking or eating hot or cold foods?

Never	Once or twice	Sometimes	Often	Every day or almost every day	Don't know
-------	---------------	-----------	-------	-------------------------------	------------

Has been irritable or frustrated?

Never	Once or twice	Sometimes	Often	Every day or almost every day	Don't know
-------	---------------	-----------	-------	-------------------------------	------------

Has been upset?

Never	Once or twice	Sometimes	Often	Every day or almost every day	Don't know
-------	---------------	-----------	-------	-------------------------------	------------

Has missed school or preschool or daycare?

Never	Once or twice	Sometimes	Often	Every day or almost every day	Don't know
-------	---------------	-----------	-------	-------------------------------	------------

Has acted shy or embarrassed?

Never	Once or twice	Sometimes	Often	Every day or almost every day	Don't know
-------	---------------	-----------	-------	-------------------------------	------------

Has avoided smiling or laughing when around other children?

Never	Once or twice	Sometimes	Often	Every day or almost every day	Don't know
Had a hard time paying attention in school or preschool or daycare?					
Never	Once or twice	Sometimes	Often	Every day or almost every day	Don't know
Has not wanted to talk/interact to other children?					
Never	Once or twice	Sometimes	Often	Every day or almost every day	Don't know
Has been anxious or fearful?					
Never	Once or twice	Sometimes	Often	Every day or almost every day	Don't know

3. FIS 8-item version

The following questions ask about effects that your child's oral condition may have on **PARENTS AND OTHER FAMILY MEMBERS**.

During the last 3 months, because of your child's teeth, lips, mouth or jaws, how often have you or another family member:

Been upset?					
Never	Once or twice	Sometimes	Often	Every day or almost every day	Don't know
Felt guilty?					
Never	Once or twice	Sometimes	Often	Every day or almost every day	Don't know
Had sleep disrupted?					
Never	Once or twice	Sometimes	Often	Every day or almost every day	Don't know
Taken time off work (e.g. due to pain, appointments, surgery)?					
Never	Once or twice	Sometimes	Often	Every day or almost every day	Don't know
Had less time for yourself or the family?					
Never	Once or twice	Sometimes	Often	Every day or almost every day	Don't know
Blamed you or another person in the family?					
Never	Once or twice	Sometimes	Often	Every day or almost every day	Don't know
Argued with you or others in the family?					
Never	Once or twice	Sometimes	Often	Every day or almost every day	Don't know
Required more attention from you or others in the family?					
Never	Once or twice	Sometimes	Often	Every day or almost every day	Don't know

Items are scored using a 5-point Likert scale (response options: ‘Never’=0; ‘Once or twice’=1; ‘Sometimes’=2; ‘Often’=3; ‘Every day or almost every day’=4). A “Don’t know” response option is provided, and this is scored as 0 in order to prevent the loss of valuable information which would occur if complete data from participants with non-response to some items was deleted.

The Global rating questions (asked before the other scales) are scored on a 5-point scale (from 1 to 5), ranging from ‘Excellent’ to ‘Poor’ and ‘Not at all’ to ‘Very much’. The global transition rating pertaining to perceptions in change in the child’s quality of life since having the SDF/placebo treatment is scored on a 5-point Likert scale scored from ‘Much improved’ to ‘Much worse’ (scored 1 to 5).

P-CPQ and FIS total and subscale scores are computed by summing the scores.

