5.2 Participant Exclusion Criteria

An individual who meets any of the following criteria will be excluded from participation in this trial:

Child:

- Hereditary generalized developmental dental defects such as Amelogenesis Imperfecta and Dentinogenesis Imperfecta.
- Known allergy/sensitivity to silver or other heavy metal ions.
- Presence of any gingival or peri-oral ulceration, abscess or stomatitis.
- Participating in the foster care system at trial initiation.
- Toothache pain at baseline (based on Dental Discomfort Questionnaire score of 1 or higher (Appendix B)).
 - Note: If toothache pain occurs after baseline, the child remains eligible to continue in the trial as long as he/she has at least one trial tooth that meets tooth inclusion/exclusion criteria.
- Demonstrated inability to comply with trial protocol requirements (determination is at the Clinical Site Investigator’s discretion).
- Rickets.
- Osteopenia or osteoporosis (e.g., Osteogenesis Imperfecta, Ehlers-Danlos Syndrome, Marfan Syndrome, etc.).
- Chronic diseases such as chronic kidney disease, leukemia, lymphoma, rheumatic disorders, etc.
- Metabolic bone disease (e.g., Galactosemia, Glycogen Storage Disease Type 1, etc.).

- Chronic glucocorticoid, anticonvulsants, chemotherapy, bisphosphonate administration.
- Hypothyroidism, hyperparathyroidism, impaired glucose tolerance, hypocalcemia or hypophosphatemia.

Tooth:

- Pain due to caries at baseline (based on DDQ score of 1 or higher, Appendix B).
 - Note: If toothache pain occurs after baseline due to a trial tooth, the tooth is removed from the trial.
- Pulpal exposure, or signs of pulpal infection (abscess, fistula, swelling).
- Mobility not associated with expected exfoliation patterns.

Parent/Legal Guardian:

- Demonstrated inability to comply with trial protocol requirements (determination is at the Clinical Site Investigator's discretion).
- Inability to read and comprehend the consent document or trial questionnaires in the translated languages available.

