12.1 Trial Hypotheses

The Primary Hypothesis:

- 38% Silver Diamine Fluoride (SDF) will arrest cavitated caries lesions (ICDAS 5 or 6) in primary teeth, measured by a change in dentin hardness, without a change in ICDAS severity score, after a single application (measured at approximately 6 months post initial application). This occurs as a result of the halting of the caries disease process, which occurs very soon after application of SDF due to its strong antimicrobial and remineralizing properties.

The Secondary Hypotheses:

- 38% Silver Diamine Fluoride (SDF) will arrest a greater proportion of cavitated caries lesions (ICDAS 5 or 6) in primary teeth after two applications, approximately 6 months apart (measured at approximately 8 months after initial SDF application).
- Lesions arrested approximately 3 months after a single application will remain stable when re-assessed at approximately 6 months.
- 38% Silver Diamine Fluoride (SDF) will decrease the proportion of children in pain, number of pain episodes associated with treated teeth for children, and pain score associated with treated teeth. The hypothesis is that SDF will do this as it is an anti-hypersensitivity agent, extremely efficient at blocking dentinal tubules, and also because it can arrest cavitated lesions, and thus decrease pain.

The Tertiary Hypotheses:

- 38% Silver Diamine Fluoride (SDF) will increase Oral Health-Related Quality of Life (OHRQoL) as a result of decreasing pain and arresting caries lesions.
- 38% Silver Diamine Fluoride (SDF) will be an acceptable treatment by parents/guardians of young children.

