Additional GLMs for binary and count outcomes and analysis of covariance models for continuous outcomes, as appropriate for each outcome above, will analyze the effects of covariates and their interactions with the treatment effect.

Aim 4 (Family-level outcomes): The P-CPQ, FIS, and satisfaction and acceptability scores will be compared between the SDF and placebo-treated groups using analysis of covariance, with trial site included as a covariate.

Additional analyses will consider the effects of covariates and their interactions with the treatment effect.

Changes in the color of treated lesions over time will be compared between treatments using a Cochran-Mantel-Haenszel chi-square test, with trial sites as the strata.

The family's experiences with ECC, child's brushing and dietary habits, and color change will be examined as additional covariates for the analyses of satisfaction and acceptability scores.

Safety: The proportion of infected trial teeth at each visit will be compared between the SDF and placebo-treated groups using a generalized estimating equation (GEE) model for binary outcomes, using an exchangeable correlation to account for possible non-independence among multiple teeth within a participant. Trial site will be included as a covariate.

The proportion of participants with adverse events (gum infection, oral mucositis, allergic reaction, anaphylaxis, nausea, vomiting, gastrointestinal pain, diarrhea; individually and the presence of any of the events) during the follow-up period will be compared between the SDF and placebo-treated groups using Cochran-Mantel-Haenszel chi-square tests, with trial sites as the strata.

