6.11.5. Tertiary Efficacy Hypotheses, Endpoints, and Analyses

The P-CPQ (Sub-Aim 4a), FIS (Sub-Aim 4a), and satisfaction and acceptability scores (Sub-Aim 4b) will be compared between the SDF and placebo-treated groups using analysis of covariance (ANCOVA). The models will include study site as a covariate due to stratified randomization by site. Additional ANCOVA models will consider the effects of covariates and their interactions with the treatment effect.

Changes in the color of treated lesions over time will be summarized by group.

The family's experiences with ECC, child's brushing and dietary habits, and color change will be examined as additional covariates for the analyses of satisfaction and acceptability scores.

The total number of episodes of pain associated with trial teeth per participant (calculated by adding all reports of pain throughout the trial verified by a clinical exam to be associated with a trial tooth) during the follow-up period and the DDQ scores will be summarized for the SDF and placebo treated groups. Due to the small number of participants with any pain, no statistical comparisons will be performed for the number of episodes of pain or the DDQ scores.

Additional analyses of the proportion of arrested lesions at 3-months, 6-months, and 8-months will extend the GEE models for binary outcomes to include covariates and their interactions with the treatment effect; covariates will include race/ethnicity, gender, age, trial site, initial ICDAS score, tooth location (anterior/posterior; as there are some data in the literature to suggest a difference in SDF efficacy) and number of affected teeth. Interactions of the covariates with treatment will be explored to examine the results for differential treatment effects. However, the analyses are not specifically powered to detect these interactions. Due to the small number of participants with any pain, no analyses which include covariate effects on the binary pain outcomes will be performed.

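### Protocol Appendix C ties SDF's effect on quality of life to change within the SDF children, at odds with the between-arm ANCOVA in Protocol 12.4 and SAP 6.11.5 (minor)

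*Protocol*

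**What the plan says.** Protocol 12.1 gives the tertiary hypothesis that SDF "will increase Oral Health-Related Quality of Life (OHRQoL) as a result of decreasing pain and arresting caries lesions". The documents then describe two ways of looking at P-CPQ.

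- **Protocol Appendix C, note on the global transition question.** The note opens by giving the question's purpose as "for assessing the responsiveness of the OHRQoL measures in children with ECC". It continues that, if SDF had helped, "we would expect to see a substantial fall in P-CPQ scores between baseline and follow-up in the children who had received the SDF". It adds: "This will be determined using the effect size, a unitless measure of change in mean score". The calculation is baseline minus follow-up, "dividing the result by the standard deviation of the mean baseline score for that group". These sentences name no contrast with placebo and no threshold for a substantial fall.
- **Protocol 12.4, Aim 4.** "The P-CPQ, FIS, and satisfaction and acceptability scores will be compared between the SDF and placebo-treated groups using analysis of covariance", with trial site as covariate. SAP 6.11.5 repeats this for Sub-Aims 4a and 4b, again naming only study site for the main model. It adds that further models will consider covariates and their interactions with treatment.

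SAP 6.11 sets the null hypothesis as no difference between treatment groups. The SAP does not mention the Appendix C effect size. Protocol 3.2.3 classes quality of life as tertiary and not intended to support labeling claims.

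**The concern.** Whether SDF improved children's lives is a causal question, and this trial has a randomised placebo arm to answer it. A fall in P-CPQ among SDF children alone shows only that their scores changed over time.

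Change common to both arms is plausible from the documents. Protocol 5.2 excludes any child with a DDQ score of 1 or higher at baseline. The DDQ items (chewing problems, avoided foods, crying at meals, night waking) overlap with P-CPQ items on pain, chewing, eating and sleep. Baseline scores may therefore be low by selection and rise later in both arms. In the other direction, both arms receive a toothbrush, fluoride toothpaste and diet and brushing advice (Protocol 7.2 and 7.3.4), and painful trial teeth are referred for care (7.3.3). The documents give no figure for the net direction.

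If an author followed Appendix C literally, a shared improvement could be described as a benefit of SDF, or a shared worsening could hide a real one. At stake is a statement about a tertiary outcome.

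**Working it through.** The plan gives no SD, effect size, power or threshold for P-CPQ, so there is no planned figure to reproduce. The 1144 children in Protocol 12.2 were sized on lesion arrest. The values below are assumptions in units of the baseline SD of individual scores.

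**What each measure estimates.** Let *c* be the improvement common to both arms and *d* the extra improvement caused by SDF.

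- Appendix C effect size in the SDF arm: (mean baseline − mean follow-up) / SD = *c* + *d*
- The same quantity in the placebo arm: *c*
- SDF-minus-placebo difference: (*c* + *d*) − *c* = *d*

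| Common change *c* | SDF effect *d* | SDF-arm effect size | Placebo-arm effect size | Between-arm difference |
|---|---|---|---|---|
| 0 | 0.3 | 0.30 | 0.00 | 0.30 |
| 0.3 (fall) | 0 | 0.30 | 0.30 | 0.00 |
| −0.3 (worsening) | 0.3 | 0.00 | −0.30 | 0.30 |
| 0.3 (fall) | 0.3 | 0.60 | 0.30 | 0.30 |

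Rows 1 and 2 give the same SDF-arm value with opposite truths. In row 3 a real benefit gives an SDF-arm value of zero. The between-arm difference equals *d* in every row.

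**Whether the planned ANCOVA is adequate.** With 1:1 allocation (Protocol 5.4) there are 1144 / 2 = 572 children per arm. Assume equal SDs at both times and a two-sided 5% level, since none is stated for tertiary outcomes.

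- Site as the only covariate: SE = √(2/572) = 0.059. For *d* = 0.3, 0.3 / 0.0591 = 5.07, so power is Φ(5.07 − 1.96) = 99.9%. For *d* = 0 the rejection rate is 5%, whatever *c* is.
- Baseline score added, with baseline-to-follow-up correlation ρ: SE = √(2(1 − ρ²)/572).

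| ρ (assumed) | SE | Reduction from 0.059, 1 − √(1 − ρ²) |
|---|---|---|
| 0.3 | 0.056 | 5% |
| 0.5 | 0.051 | 13% |
| 0.7 | 0.042 | 29% |

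The site-only model is valid because allocation was randomised. Adding the baseline score improves precision and makes the ANCOVA address the change from baseline that Appendix C is concerned with.

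**The case against.** The strongest reply is that Appendix C was never meant to decide anything. The note opens as a check of instrument responsiveness, and a standardised within-group change is an ordinary statistic for that purpose. To say that a fall would be expected if SDF worked is a one-way implication: it does not say that a fall proves SDF worked. The phrase about that group's baseline SD also fits calculating the statistic in each arm. Protocol 12 leaves detailed procedures to the SAP, and both analysis sections compare the arms.

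Most of this stands and is why the point is minor. What remains is the sentence saying the matter will be determined by the effect size. Its subject is whether SDF improved lives, and the expected fall is in SDF children. The same note calls the transition question an outcome in its own right, so it mixes measurement checks with outcome assessment. Nothing in either document says which use governs. Because the main ANCOVA names only site, the Appendix C formula is also the only P-CPQ analysis explicitly defined on change from baseline.

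A reader might infer more than the documents support:

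- **That the trial will judge SDF's effect from the SDF arm alone.** Protocol 12.4 and SAP 6.11.5 both plan a between-arm comparison. No within-arm significance test or cut-off is planned.
- **That the SAP adopts the Appendix C rule.** SAP 3.3 cites the appendix as the source of the questionnaires. SAP 9 lists changes from the protocol-specified analyses, and an appendix note missing from that list does not show that a competing rule survives.
- **That the divisor is a standard error.** The text says standard deviation; the reference to the mean is awkward wording and needs only an editorial correction.

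**Conclusion.** The point holds as a minor conflict between Protocol Appendix C and the analysis sections. Followed as written, the Appendix C measure equals the common change plus the SDF effect, so its error as an estimate of SDF's effect is exactly the common change. That result needs no assumption about size. The 0.3 SD values are illustrations, because the documents give neither the common change nor the P-CPQ variability, and the forces they describe act in opposite directions.

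The primary and key secondary conclusions are unaffected. Quality of life is tertiary, outside the hierarchical testing of two key secondary endpoints in SAP 6.11.4, and not for labeling. The planned ANCOVA removes common change and gives a valid between-arm answer even with site alone. The remaining risk is a misattributed or missed quality-of-life statement if the effect size is reported as evidence of benefit.

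**What to change.** 1. In Appendix C, state that the within-group effect size is descriptive and used only to check instrument responsiveness. Define it as change divided by the SD of individual baseline scores. Report it for both arms, or with arms pooled by global transition category.
2. In Appendix C and SAP 6.11.5, state that SDF's effect on P-CPQ and FIS is judged only by the SDF-minus-placebo difference from the planned ANCOVA, with its confidence interval.
3. In SAP 6.11.5, add the baseline score of the scale being analysed as a covariate beside site in the main model.
4. Record the change in SAP 9 before the analysts are unmasked.

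The cost is a few sentences and one extra model term. No new data are needed, since P-CPQ and FIS are already collected at baseline. The downside is that the reported SDF effect may look smaller than the within-arm change.
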